7.2.2 Safety and tolerability assessments

Safety will be monitored by assessing the procedures listed below as well as collecting all adverse events at every visit. All safety assessments should be performed pre-dose unless specified otherwise.

7.2.2.1 Physical examination

A complete physical examination that evaluates all major organ systems will be performed at Screening/baseline. Subsequent physical exams may be limited and should be focused on sites of disease to explore clinical signs and symptoms.

Significant findings that were present prior to the signing of informed consent must be included in the Relevant Medical History/Current Medical Conditions page on the patient's eCRF. Significant new findings that begin or worsen after informed consent must be recorded on the Adverse Event page of the patient's eCRF.

Physical exams to be performed are outlined in [Table 7-1](#).

7.2.2.2 Vital signs

Vital signs (heart rate, blood pressure and temperature) will be obtained in the sitting position, or as appropriate prior to any blood collection.

Vital signs to be performed per [Table 7-1](#).

7.2.2.3 Performance status

Assessment of ECOG Performance Status will be performed at screening and regularly throughout the whole study period irrespective of the time of dosing

Performance status to be performed per [Table 7-1](#) and [Table 7-3](#).

Table 7-3 ECOG performance status

Grade ECOG status
0 Fully active, able to carry on all pre-disease performance without restriction
1 Restricted in physically strenuous activity but ambulatory and able to carry out work of a light or sedentary nature e.g., light house work, office work
2 Ambulatory and capable of all self-care but unable to carry out any work activities. Up and about more than 50% of waking hours
3 Capable of only limited self-care, confined to bed or chair more than 50% of waking hours
4 Completely disabled. Cannot carry on any self-care. Totally confined to bed or chair
5 Dead

7.2.2.4 Height and Weight

Height in centimeters (cm) and body weight in kilogram (kg). Height and weight to be performed per [Table 7-1](#).

7.2.2.5 Laboratory evaluations

Sites will use their local laboratories for the analysis of all safety lab samples, collected at the time points indicated as per [Table 7-1](#). More frequent assessments may be performed if clinically indicated, or at the investigator's discretion and these should be recorded on the Unscheduled Visit eCRF's.

Abnormal laboratory values that are clinically relevant (e.g., require an interruption or delay to study treatment, lead to clinical symptoms, or require therapeutic intervention) must be documented in the Adverse Event eCRF.

Novartis will be provided with a copy of the site's local laboratory certification and tabulation of the normal ranges for each parameter required at study start and should be kept up to date on an ongoing basis. In addition, if at any time a patient has laboratory parameters obtained from a different outside laboratory, Novartis must be provided with a copy of the certification and a tabulation of the normal ranges for that laboratory.

Table 7-4 Local Clinical Laboratory Parameters Collection Plan

Test Category	Test Name
Hematology	White blood cell count (WBC) with differential (neutrophils, lymphocytes, monocytes, eosinophils, and basophils), hemoglobin (Hgb) and platelet count.
Biochemistry with fasting glucose	Sodium, potassium, urea or BUN, creatinine, fasting glucose, calcium (or corrected calcium), magnesium, phosphorous, total protein and albumin.
	AST (SGOT), ALT (SGPT), total bilirubin, direct bilirubin, GGT and alkaline phosphatase, Amylase, lipase and LDH.
Fasting Lipid Panel	Total cholesterol, LDL-cholesterol, HDL-cholesterol and triglycerides
Coagulation	PT/PTT, International normalized ratio [INR]
Urinalysis	Macroscopic Panel (Dipstick) (Color, Bilirubin, Blood, Glucose, Ketones, Leukocytes esterase, Nitrite, pH, Protein, Specific Gravity, Urobilinogen)
	If there are any significant findings on the dipstick then a microscopic evaluation should be measured: Microscopic Panel (WBC and RBC sediments, Casts, Crystals, Bacteria, Epithelial cells)

7.2.2.5.1 Hematology

Complete blood count (CBC) with differential - white blood count (WBC), neutrophil count (including bands], lymphocyte, monocyte, eosinophil, and basophil counts, hemoglobin, and platelet count. Hematology collections to be performed per [Table 7-1](#). Hematology tests are to be performed according to the Visit Schedules outlined in [Table 7-1](#). For details of the Hematology panel refer to [Table 7-4](#).

7.2.2.5.2 Clinical chemistry

Sodium, potassium, chloride, bicarbonate, urea or BUN, creatinine, glucose, fasting glucose (at least 2 hours fasting), AST (SGOT), ALT (SGPT), total bilirubin (if a total bilirubin elevation

≥Grade 2 occurs then direct and indirect bilirubin should be measured), LDH, albumin, calcium (corrected for serum albumin), magnesium, phosphate, alkaline phosphatase and fasting lipid panel (at least 8 hours). Clinical chemistry visit schedules are outlined in [Table 7-1](#). For details of the Chemistry panel refer to [Table 7-4](#).

7.2.2.5.3 Urinalysis

Urinalysis is to be performed according to the Visit Schedules outlined in [Table 7-1](#). For details of the urinalysis panel refer to [Table 7-4](#).

7.2.2.5.4 HBV testing

Prior to enrollment, the categories of patients listed in [Section 5.1.1](#) should be tested for hepatitis B serologic markers and viral load: HBV-DNA HBsAg, HBc Ab, and HBs Ab. HBV DNA monitoring should be done depending on results from serologic markers and viral load as listed in HCV testing.

Patients with hepatitis C risk factors and additional patients at the discretion of the investigator should be tested for HCV RNA-PCR test at screening. For a list of hepatitis C risk factors, refer to [Section 5.1.2](#). Follow-up testing will be performed, as per the visit schedule, only if the patient has a history or is positive at baseline, or both.

7.2.2.5.5 Hepatic safety markers

An additional blood sample is requested from patients in response to rise in ALT/AST or in total bilirubin (as described below) if this rise occurs outside of the scheduled collection dates:

- In patients with normal AST and ALT and total bilirubin at baseline that present a rise of AST or ALT \geq grade 2 with total bilirubin $>2 \times$ ULN without evidence of cholestasis (defined as: ALP elevation $>2.0 \times$ ULN with R value [ALT/ALP in \times ULN] <2 in patients without bone metastasis, or elevation of ALP liver fraction in patients with bone metastasis).

OR

- For patients with elevated baseline AST or ALT or total bilirubin that present [AST or ALT $>2 \times$ baseline AND $>3.0 \times$ ULN] OR [AST or ALT $8.0 \times$ ULN]- whichever is lower- combined with [total bilirubin $2 \times$ baseline AND $>2.0 \times$ ULN]

OR

- ALT or AST $>8 \times$ ULN without bilirubin increase

Analysis of samples will be performed based on results of ALT/AST and total bilirubin, with the aim to better understand the underlying mechanism of any observed hepatotoxicity.

7.2.2.6 Cardiac assessments

7.2.2.6.1 Electrocardiogram (ECG)

Standard triplicate 12-lead ECGs will be performed after the patient has been resting for 5-10 minutes prior to each time point indicated in [Table 7-5](#).

TriPLICATE ECGs should be taken approximately 2-minutes apart. The combined QTcF values from these 3 ECGs will be averaged to provide a single value for each time point. Eligibility

will be based on the average of the triplicate ECG conducted at screening. In order for accurate evaluation of baseline QTcF, a total of three 12-lead ECGs will be performed within 7 days prior to registration (at screening between Day -7 and Day -1).

Note: All study ECGs, should be submitted to the designated CRO immediately.

Note: To ensure ECG evaluation is received for eligibility assessment, it is advisable to perform the ECG at least 24 hours prior the scheduled enrollment date as it takes at least 24 hours to receive central read.

If an abnormal ECG or QTcF value of ≥ 481 ms is obtained at any time after enrollment, management guidelines detailed in Table 6-7 must be followed.

An unscheduled ECG may be repeated at the discretion of the investigator at any time during the study and as clinically indicated. Unscheduled ECGs with clinically significant findings should be collected in triplicate.

Local cardiologist ECG assessment may be performed at any time during the study at the discretion of the investigator.

In the event that a QTcF value of ≥ 501 ms is observed or if an unscheduled ECG is performed for safety reasons, it is recommended to collect a time-matched blood sample for PK and record the time and date of the last study drug intake to determine plasma levels of ribociclib and any other identified metabolites.

Table 7-5 Central ECG Collection Plan

Cycle	Patients	Day	Sampling Time ^a ^b	ECG Type
Screening	All	-7 to -1	Anytime	Triplet 12 Lead
1	All	Day 15	pre-dose ^d	Triplet 12 Lead
			2 h post-dose (± 15 min)	Triplet 12 Lead
			4 h post-dose (± 15 min)	Triplet 12 Lead
			pre-dose ^d	Triplet 12 Lead
2	All	Day 1	2 h post-dose (± 15 min)	Triplet 12 Lead
			4 h post-dose (± 15 min)	Triplet 12 Lead
			pre-dose ^d	Triplet 12 Lead
	All	Day 15	2 h post-dose (± 15 min)	Triplet 12 Lead
			4 h post-dose (± 15 min)	Triplet 12 Lead
			pre-dose ^d	Triplet 12 Lead
3	All	Day 1	pre-dose ^d	Triplet 12 Lead
4	All	Day 1	pre-dose ^d	Triplet 12 Lead
5	All	Day 1	pre-dose ^d	Triplet 12 Lead
6	All	Day 1	pre-dose ^d	Triplet 12 Lead
9th and every 3rd cycle ^c	For patients with QTcF ≥ 481 ms at any time prior to cycle 7	Day 1	pre-dose	Single 12 Lead

Cycle	Patients	Day	Sampling Time ^{a, b}	ECG Type
Unscheduled			As clinically indicated	TriPLICATE 12 Lead
End of Treatment			Within 15 days of last dose	TriPLICATE 12 Lead

^a. All measurement times are relative to dose of ribociclib unless otherwise specified.

^b. If both ECG and PK sample are scheduled at the same time, the PK sample should be taken immediately (within 1 hour) after ECG assessment

^c. Pre-dose ECG on the first day of every cycle. Additionally, 2 h post-dose in every 3rd cycle (i.e. Cycle 9, 12, 15, 18, etc.).

^d. The exact date and time of dosing must be recorded on the appropriate eCRF.

All ECGs including unscheduled triplicate ECGs with clinically relevant findings, collected during the study should be transmitted to a central laboratory and will be centrally reviewed by an independent reviewer. Each ECG tracing should be labeled with the study number, patient number, date, and kept in the source documents at the study site. Clinically significant ECG abnormalities present at screening when the patient signs informed consent should be recorded on the relevant medical history/current medical conditions eCRF page. New or worsened clinically significant findings occurring after informed consent must be recorded on the Adverse Events CRF page

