A minimum of approximately 60 evaluable patients (30 per group(Group 1 and Group 2)) are required for Phase II of this study to evaluate clinical benefit rate at 24 weeks.

In each phase II group (1 and 2), if 8 or more patients show clinical benefit at 24 weeks then the null hypothesis will be rejected and the study will demonstrate significant clinical benefit.

RP2D:

[figure not shown]
Following completion of the phase I, dose escalation portion of this trial, it was determined that the RP2D to be explored in group 1 of phase II is as follows:

300mg ribociclib (daily) + 2.5mg everolimus (daily) + 25mg exemestane (daily)

RP2D for group 2 of phase II was determined after completion of cohort C, of phase I, as follows:

200mg ribociclib (daily) + 5mg everolimus (daily) + 25mg exemestane (daily) During Phase II, all patients must have progressed on any CDK 4/6 inhibitor. Prior CDK 4/6 inhibitor will be defined as disease progression while on, or within one month of discontinuing any CDK 4/6 inhibitor (i.e. palbociclib, ribociclib, or abemaciclib).

Figure 4-1 Study design

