Management of everolimus specific adverse reactions may require temporary dose reduction and/or interruption of everolimus therapy longer than 3 weeks. Recommendations for dose interruption of everolimus longer than 3 weeks in the management of everolimus specific adverse reactions are summarized in [Table 6-7](#). Clinical judgment of the treating physician should guide the management plan of each patient based on individual benefit/risk assessment ([USA Afinitor® PI 2012](#)).

Table 6-7 Dose modification guidelines for ribociclib (if everolimus is held longer than 3 weeks for pneumonitis)

	Ribociclib	Exemestane
	Dose	Dose
Starting dose	400 mg daily	25 mg
First dose reduction	200mg daily	
Second dose reduction	200mg 3 weeks on, 1 week off	

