6.4.3.2 Ribociclib/everolimus dose modification and management for QTcF prolongation

Table 6-9 Ribociclib/everolimus dose modification and management for QTcF prolongation

(see [Table 6-5](#) and [Table 6-6](#) for dose reduction guide)

Adverse drug reaction	Severity	Dose adjustment and management recommendations
QTcF prolongation	For All Grades	Check the quality of the ECG and the QT value and repeat if needed.

Adverse drug reaction	Severity	Dose adjustment and management recommendations
		
Perform analysis of serum electrolytes (K+, Ca++, Phosphorus, Mg++). If outside of normal range, hold ribociclib and everolimus, correct with supplements or appropriate therapy as soon as possible, and repeat electrolytes until documented as normal.
 
Review concomitant medication usage for the potential to inhibit CYP3A4 and/or to prolong the QT interval.
 
Check compliance with correct dose and administration of study treatment
 
Consider collecting a time matched PK sample; record date and time of last study drug intake.

	Grade 1 QTc 450-480 ms	
Perform steps 1-4 as directed in "For All Grades." No dose adjustment required.

	Grade 2 QTc 481-500 ms	
Hold ribociclib and everolimus. Perform steps 1-4 as directed in "For All Grades."
 
Repeat ECG as clinically indicated until the QTcF returns to <481 ms. Restart ribociclib with dose reduced by 1 dose level.
 
If QTcF \geq 481 ms recurs, ribociclib should be reduced again by 1 dose level.
 
Repeat ECGs 7 days and 14 days after dose resumption of study treatment (then as clinically indicated) for any patients who had therapy interrupted due to QTcF \geq 481 ms.

	Grade 3 QTc \geq 501 ms on at least two separate ECGs	
Hold ribociclib and everolimus. Perform steps 1-4 as directed in "For All Grades."
 
Transmit ECG immediately and confirm prolongation/

Adverse drug reaction	Severity	Dose adjustment and management recommendations

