6.4.6 Guidance for all other adverse reactions

Consider performing an analysis of serum potassium, calcium, phosphorus, and magnesium for all adverse reactions, if indicated. If electrolyte values are outside of the normal range, interrupt ribociclib/everolimus administration, correct electrolytes with supplements or appropriate therapy as soon as possible, and repeat electrolyte testing until documented normalization of the electrolytes.

Table 6-16 Ribociclib/everolimus dose adjustment and management recommendation for all other adverse reactions

(see [Table 6-5](#) and [Table 6-6](#) for dose reduction guide)

Grade/Severity	Dose adjustment and management recommendations
Grade 1	No dose adjustment- maximize AE management
Grade 2	Dose interruption of ribociclib/everolimus until recovery to Grade ≤1 Initiate appropriate medical therapy and monitor Re-initiate study treatment at the same dose If the same toxicity recurs at Grade 2, interrupt ribociclib/everolimus until recovery to Grade ≤1. Re-initiate study treatment at the next lower dose level.
Grade 3	Hold both everolimus and ribociclib until it resolves to ≤Grade 1. Initiate appropriate medical management and monitor Re-initiate study treatment at the next lower dose level If toxicity recurs at grade 3, discontinue study treatment
Grade 4	Discontinue study treatment
Additional recommendations (see supplementary management brochure for further recommendations):	
Nausea: Ensure adequate hydration or fluid repletion. Consider performing an analysis of serum potassium, calcium, phosphorus and magnesium, if indicated. If electrolyte values are below LLN, interrupt ribociclib, correct electrolytes with supplements as soon as possible, and repeat electrolyte testing until documented normalization.	

Diarrhea: At the first sign of loose stools (Grade 1), initiate loperamide. Patient should remain well hydrated. Fluids and electrolytes should be replaced as needed. Consider performing an analysis of serum potassium, calcium, phosphorus and magnesium, if indicated. If electrolyte values are below LLN, interrupt ribociclib, correct electrolytes with supplements as soon as possible, and repeat electrolyte testing until documented normalization.

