6.5.3 Permitted concomitant therapy requiring caution and/or action while on study

Permitted medications to be used with caution combined ribociclib + everolimus + exemestane treatment in this study ([Appendix 1, Table 14-2](#)) are listed below. These medications should be excluded from patient use if possible. If they must be given based on the investigator's judgment, then use with caution and consider a ribociclib interruption if the concomitant medication is only needed for a short time:

- Moderate inhibitors or inducers of CYP3A4/5.
- Sensitive substrates of CYP3A4/5 that do not have narrow therapeutic index.
- Strong inhibitors of BSEP.
- Medications that carry a possible risk for QT prolongation.
- Sensitive substrates of the renal transporters, MATE1 and OCT2.
- Sensitive substrates of BCRP (has a potential to increase exposure to substrates of these transporters, although no animal or clinical data are available to support these statements)

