Sensitive CYP3A4/5 substrates ¹	Alpha-dihydroergocryptine, apixaban, aprepitant, atorvastatin, avanafil, bosutinib, brotizolam, budesonide, buspirone, cobimetinib, darifenacin, dasatinib, ebastine, eletriptan, eplerenone, everolimus, felodipine, fluticasone, grazoprevir, ibrutinib, isavuconazole, ivabradine, ivacaftor, lumefantrine, lurasidone, maraviroc, midazolam, midostaurin, naloxegol, neratinib, perospirone, quetiapine, ridaforolimus, rivaroxaban, sildenafil, simeprevir, ticagrelor, tilidine, tolvaptan, triazolam, ulipristal, vardenafil, venetoclax, vicriviroc, voclosporin-
BSEP inhibitors	Alectinib, atorvastatin, bromocriptine, candesartan, clobetasol, clofazimine, dabigatran, dipyridamole, glyburide, grazoprevir, ledipasvir, mifepristone, pioglitazone, reserpine, rifamycin, simeprevir, telmisartan, timcodar, troglitazone, valinomycin, velpatasvir

Category	Drug Name
Medications that carry a possible risk for QT prolongation ²	Alfuzosin, apomorphine, aripiprazole, artenimol+piperaquine, asenapine, atazanavir, atomoxetine, bedaquiline, bendamustine, bortezomib, bosutinib, buprenorphine, cabozantinib, capecitabine, ceritinib, clomipramine, crizotinib, clozapine, cyamemazine (cyamepromazine), dabrafenib, dasatinib, degarilix, delamanid, desipramine, dexmedetomidine, dolasetron, efavirenz, eliglustat, epiubicin, eribulin mesylate, ezogabine(retigabine), famotidine, felbamate, fingolimod, flupentixol, gemifloxacin, granisetron, hydrocodone-ER, iloperidone, imipramine (mepipramine), isradipine, ketanserin, lapatinib, lenvatinib, leuprolide, loperamide, lithium, melperone, midostaurin, mifepristone, mirabegron, mirtazapine, moexipril/HCTZ, necitumumab, nilotinib, norfloxacin, nortriptyline, nusinersen, ofloxacin, lanzapineosimertinib, oxytocin, paliperidone, palonosetron, panabinstat, pasireotide, pazopanib, perflutren lipid microspheres, perphenazine, pilsicainide, pimavanserin, pipamperone, promethazine, prothipendyl, quetiapine, ranolazine rilpivirine, risperidone, romidepsin, sertindole, sorafenib, sunitinib, tamoxifen, telavancin, tetrabenazine, tipiracil/trifluridine, tizanidine, tolterodine, oremifene, trimipramine, tropisetron, vardenafil, vemurafenib, venlafaxine, vorinostat, ziprasidone
MATE1/2 substrates ³	Acyclovir, cephalexin, cimetidine, fexofenadine, ganciclovir, glycopyrronium, metformin, pindolol, plisicainide, ranitidine, topotecan, varenicline

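### The ECG section makes Table 6-7, a pneumonitis table with no QT steps, mandatory for QTcF of 481 ms or more; the protocol's QTcF steps are in Table 6-9

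*Protocol*

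**What the plan says.** **QTcF.** Protocol section 7.2.2.6.1 sets a trigger: an abnormal ECG, or a QTcF of at least 481 ms, at any time after enrollment. For that trigger, "management guidelines detailed in Table 6-7 must be followed".

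Table 6-7, in section 6.4.1.1, is titled "Dose modification guidelines for ribociclib (if everolimus is held longer than 3 weeks for pneumonitis". Table 6-9, in section 6.4.3.2, is titled "Ribociclib/everolimus dose modification and management for QTcF prolongation". For a QTc of 481 to 500 ms, Table 6-9 holds ribociclib and everolimus, repeats the ECG until QTcF is below 481 ms, and then says "Restart ribociclib with dose reduced by 1 dose level".

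**Loperamide.** The diarrhoea note under Table 6-16 (section 6.4.6) says "At the first sign of loose stools (Grade 1), initiate loperamide". Table 14-2 (Appendix 1) lists loperamide in its row of drugs with a possible QT risk: "lapatinib, lenvatinib, leuprolide, loperamide, lithium". Section 6.5.3, which governs the Table 14-2 drugs, says "These medications should be excluded from patient use if possible". If the investigator judges such a drug necessary, section 6.5.3 asks for caution, and for a ribociclib interruption to be considered when the need is short.

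**The concern.** Section 7.2.2.6.1 is where a site looks when a prolonged QTcF is reported, and its wording is mandatory. The table it names contains nothing about QT. QT prolongation is a named ribociclib risk in the protocol, and updating QTcF management is the first of the listed purposes of Amendment 3. A wrong table number in this sentence is therefore a fault in an operative safety instruction. What is at stake is delay or inconsistency between sites in carrying out the QTcF steps.

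The loperamide passages raise a milder form of the same problem. One tells the site to start the drug at the first loose stool, another tells it to keep the drug away from patients where possible, and neither refers to the other.

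**Working it through.** No statistical quantity in the plan depends on this point, so the check is a comparison of text followed by a short count for scale.

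**Step 1. What the trigger needs and what each table supplies.**

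| Item | Table 6-7 | Table 6-9 |
|---|---|---|
| Condition for use | Everolimus held more than 3 weeks for pneumonitis | QTcF prolongation |
| QTcF thresholds | None | 450-480, 481-500, and 501 ms or more |
| Drug hold for QTcF | None | Ribociclib and everolimus held from 481 ms |
| Electrolyte check | None | Yes, at all grades |
| Repeat ECG | None | Yes, including at 7 and 14 days after resumption |
| Ribociclib content | Starts at 400 mg daily, with two reduction steps | One-level reduction, or discontinuation, by grade |

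The 481 ms in section 7.2.2.6.1 matches the lower bound of the 481-500 ms row in Table 6-9. It matches nothing in Table 6-7.

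**Step 2. Is this an extraction artefact?** No. The list of tables and the tables themselves agree on both titles. The entries for Amendment 3 also name Table 6-9 as the table updated for QTcF prolongation. A likely origin is renumbering. The Amendment 1 entries call the pneumonitis management table 6-11, and it is now 6-13. The same shift of two would turn an old 6-7 into 6-9. This is an inference, and the finding does not depend on it.

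**Step 3. Does the reference assign a dose?** Table 6-7 carries its own condition. A patient whose only finding is a QTcF of 481 ms or more has not had everolimus held over 3 weeks for pneumonitis, so no row of Table 6-7 applies. The reference leads to no QT action; it does not lead to 400 mg.

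**Step 4. Loperamide, for scale.** Treatment-related diarrhoea of any grade:
- This trial, cohorts A and B (Table 1-7): 1 of 16. The Phase II total is 79 (46 + 33, SAP section 4). 1/16 × 79 = 4.9, about 5 patients.
- The Phase Ib triplet study, three weeks on and one week off (Table 1-6): 14 of 77. 14/77 × 79 = 14.4, about 14 patients.

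These counts cover related events only. The instruction applies to any loose stools, so the number meeting it could be higher.

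**Step 5. QT events, for scale.** Section 1.2.5.1.2 reports no QT prolongation in the 16 patients of cohorts A and B. The exact two-sided 95% upper limit for 0 of 16 is 1 − 0.025^(1/16) = 1 − 0.794 = 0.206. Sixteen patients therefore neither show a problem nor exclude one.

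**The case against.** The strongest reply is that this is a clerical slip with little practical effect. Table 6-9 has a plain title, appears in the list of tables, and carries its own thresholds, so it governs QTcF whether or not section 7.2.2.6.1 names it. A site that opens Table 6-7 sees pneumonitis in the title and will probably look further. This stands, and it limits the consequence. It does not make the mandatory sentence correct.

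A reader might infer that a patient with prolonged QTcF is being sent to a higher ribociclib dose. The documents do not support that, because Table 6-7 is conditional on a pneumonitis hold. Comparing 400 mg with the Phase II doses would measure an exposure that the error does not create.

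A reader might also infer that the protocol prohibits loperamide and prescribes it at once. It does not. Section 6.5.3 is a list of permitted drugs requiring caution, loperamide is absent from the prohibited list (Table 14-1), and section 6.5.1 allows anti-diarrhoeals and refers to Appendix 1. The diarrhoea note has its own safeguard: electrolytes are considered, and ribociclib is interrupted if they are low. A site could follow both passages. What remains is that starting at Grade 1 and excluding if possible pull in different directions without a cross-reference.

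Finally, a reader might expect a distorted safety comparison between the two Phase II groups. No formal comparison is planned. SAP section 3.8 summarises safety tables overall for Phase II, section 3.8.4.1.1 does so for most ECG summaries, and the by-group safety tables are descriptive.

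**Conclusion.** The cross-reference in section 7.2.2.6.1 is wrong as written. It makes mandatory, for an abnormal ECG or QTcF of 481 ms or more, a table with no QT content, while the protocol's QTcF steps are in Table 6-9. This rests on the current operative text alone.

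The size is modest. The instruction fails to guide the site but assigns no dose, and no planned analysis is shown to be affected. The 15.7% rate of QT prolongation in single-agent patients (50 to 1200 mg, regardless of causality; section 1.2.1.4.1) should not be read as a forecast, since it comes from other doses and another regimen. This trial's own figure is 0 of 16.

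The loperamide point is secondary: an unreconciled tension between permitted-with-caution and routine use. It would touch about 5 to 14 of 79 patients if either small source of related-diarrhoea rates carried over to Phase II.

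**What to change.** Issue a protocol clarification and a site notice that reconcile the table reference in section 7.2.2.6.1 with the protocol's QTcF table, Table 6-9. In the same notice, reconcile or cross-refer the diarrhoea note under Table 6-16 with sections 6.5.1 and 6.5.3 and Table 14-2, so that a site reads one consistent instruction on loperamide and on any linked ribociclib interruption. Which clinical rule applies is for the sponsor to state; this review takes no position on it.

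The cost is two wording corrections and one communication to sites. Sample size, endpoints and analyses do not change.

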6.2.4.2 Additional dosing guidelines for scheduled visit days

On days with PK, ECG sampling, chemistry and/or lipid profile sampling as outlined in [Table 7-1](#), the following additional guidelines should be followed:

- On a day when PK blood collection is scheduled at the clinic, patients must take study treatment in the clinic under the supervision of the Investigator or designee. On all other days patients may take the study treatment at home.
- The patient must be fasting for at least 8 hours prior to cycle visits that include fasting glucose and lipid profile samples. Coffee, tea and water without milk and sugar (or artificial sweeteners) are allowed.
- If a pre-dose ECG measurement should be collected, then the ECG measurement should occur before dosing of the study treatment.
- When both PK and ECG are required, please complete the ECG prior to PK draw.
- Post-dose ECGs and PKs should be collected after dosing of the study treatment. ECG will be performed according to [Section 7.2.2.6](#) and [Table 7-5](#).
- Pre-dose samples should be drawn prior to dosing. The sampling time of the PK samples and the dosing time must be precisely recorded in the eCRF.
- Post-dose PK samples should be collected after dosing of the study treatment. PK sample collection will be performed according to [Table 7-6](#).

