				Cycle 1	Cycle 2		Cycle 3		Subsequent cycles	End of study treatment (EOT)	Safety follow-up	Efficacy follow-up		
Visit name			Screening											
Study days			-21 to -1	1	15	1	15	1	1	Within 15 days from last dose	Last dose + 30 days	Every 8 weeks (if applicable)	Every 6 months	
Coagulation	D	7.2.2.5	X		As clinically indicated					X				
Urinalysis	D	7.2.2.5.3	X	X ¹				X		X				
Tumor assessment														
Tumor evaluation (RECIST 1.1)	D	7.2.1.1	X	CT/MRI Chest, Abdomen, Pelvis +/- whole body bone scan +/- X-ray Every 8 weeks first day of study treatment for the first 12 months, and then every 12 weeks thereafter until disease progression										
Cardiac assessment														
ECG (standard 12-lead)	D	7.2.2.6.1	X (Must be completed between days -7 to -1)		X	X	X	X	X	For all cycles up to Cycle 6				
ECHO or MUGA	D	7.2.2.6.2	X	As clinically indicated										
Safety														
Adverse events	D	8.1	X	Continuous				X	X					
Pharmacokinetics														
PK	D	7.2.3		X	X	X	X	X						

	Category	Reference to protocol section	Screening phase	Treatment phase						Post treatment follow-up phase			Survival phase
				Cycle 1	Cycle 2	Cycle 3	Subsequent cycles	End of study treatment (EOT)	Safety follow-up	Efficacy follow-up	End of post-treatment follow-up		
Visit name			Screening										Survival follow-up
Study days			-21 to -1	1	15	1	15	1	1	Within 15 days from last dose	Last dose + 30 days	Every 8 weeks (if applicable)	Every 6 months
Study Drug administration													
ribociclib	D	6.2.4.1		Daily									
everolimus	D	6.2.4.1		Daily									
exemestane	D	6.2.4.1		Daily									
dexamethasone	D	6.3.1.1		TID through Cycle 2									
Discontinuation													
New antineoplastic therapies after discontinuation	D	7.1.6								X	X		

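### Table 7-5 sets two pre-dose ECG frequencies after Cycle 6 for patients with earlier QTcF of at least 481 ms: every third cycle in the row, every cycle in footnote c

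*Protocol*

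**What the plan says.** Protocol Table 7-5 is the central ECG collection plan. It covers all patients through Cycle 6. After that, one row covers patients with a QTcF of 481 ms or more at any time before Cycle 7. It lists a single 12-lead pre-dose ECG on Day 1 of the "9th and every 3rd cycle". That label carries footnote c: "Pre-dose ECG on the first day of every cycle. Additionally, 2 h post-dose in every 3rd cycle". The footnote lists Cycles 9, 12, 15, 18 and so on, and attaches that list to the 2 h post-dose ECG only.

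Other parts of the protocol do not settle the frequency:

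- Section 6.2.4.2 defers to Table 7-5 for ECG performance: "Post-dose ECGs and PKs should be collected after dosing of the study treatment. ECG will be performed according to".
- The ECG line of Table 7-1 ends at "For all cycles up to Cycle 6".
- Table 6-9, for QTc 481-500 ms, asks for event-driven checks: "Repeat ECGs 7 days and 14 days after dose resumption of study treatment (then as clinically indicated".

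Section 7.2.2.6.1 also states that if an abnormal ECG or a QTcF of 481 ms or more "is obtained at any time after enrollment, management guidelines detailed in Table 6-7 must be followed". The title of Table 6-7 is "Dose modification guidelines for ribociclib (if everolimus is held longer than 3 weeks for pneumonitis".

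**The concern.** The row and its own footnote give different routine monitoring for the same patients. One site could check the pre-dose ECG every 84 days and another every 28 days, and both could point to Table 7-5.

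These patients have already crossed the protocol's action threshold and may still be taking ribociclib daily. In Group 2, Table 6-6 keeps ribociclib at 200 mg daily through both dose reductions. Amendment 3 states that ribociclib prolongs QT in a concentration-dependent way and gives QTcF management as its first purpose, so the schedule that follows such an event should be unambiguous.

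The wrong table reference concerns the same threshold. A site that follows the mandatory instruction literally reaches a pneumonitis table whose starting ribociclib dose is 400 mg daily, above both Phase II doses (300 mg and 200 mg), and which contains no QTcF rule.

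**Working it through.** The documents state no ECG count, so there is no planned figure to reproduce. The check counts cycles under each text, assuming 28-day cycles without delay.

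**Inputs**

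- Row of Table 7-5: Cycle 9, then every third cycle.
- Footnote c: pre-dose every cycle, plus 2 h post-dose in Cycles 9, 12, 15, 18, etc.
- Population fixed before Cycle 7, so the footnote taken literally starts at Cycle 7. A start at Cycle 9 is shown as the narrower reading.

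**Pre-dose ECGs after Cycle 6 for one such patient**

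| Treated through | Row | Footnote c from Cycle 7 | Footnote c from Cycle 9 |
|---|---|---|---|
| Cycle 9 | 1 | 3 | 1 |
| Cycle 12 | 2 | 6 | 4 |
| Cycle 18 | 4 (Cycles 9, 12, 15, 18) | 12 | 10 |

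**Intervals.** Day 1 of cycle c is study day (c − 1) × 28 + 1.

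- Cycle 6: 5 × 28 + 1 = 141. Cycle 7: 6 × 28 + 1 = 169. Cycle 9: 8 × 28 + 1 = 225.
- First gap after Cycle 6 Day 1 under the row: 225 − 141 = 84 days.
- Under the footnote from Cycle 7: 169 − 141 = 28 days.
- If the footnote starts at Cycle 9, the first gap is 84 days under both texts. Later gaps still differ, 84 against 28 days.

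**Can the footnote mean every such third cycle?** No. It sets an every-cycle pre-dose ECG against an additional 2 h ECG every third cycle, and names the cycles only for the second.

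**How many patients?** The documents do not say. As an illustration only:

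- Phase I Cohorts A and B had 0 of 16 patients with QT prolongation (Protocol 1.2.5.1.2). The exact 95% upper limit is 1 − 0.025^(1/16) = 0.206.
- SAP Section 4 gives 46 + 33 = 79 Phase II patients.
- Taking the share still treated after Cycle 6 as 10% to 30% (the null and alternative 24-week clinical benefit rates), the upper limit gives 79 × 0.206 × 0.10 = 1.6 to 79 × 0.206 × 0.30 = 4.9 patients. The lower end is 0.

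**Not counted as conflicts.** The row as read shows no 2 h post-dose ECG, but the table layout is disturbed just above it and a line may have been lost. The row's single 12-lead entry is specific and is taken to govern over the general triplicate sentence.

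**The case against.** The strongest reply is that a site can comply with both texts: following the footnote also meets the row. The footnote is the more detailed text, and the row label can be seen as marking the 2 h post-dose cycles. On that view this is poor layout. The reply helps in choosing the fix. It does not remove the problem, because a site that follows the row alone also has a written basis, and no text ranks one above the other.

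A second point is that 4 against 12 is the widest contrast. Neither text says from Cycle 7, and Cycle 18 Day 1 is study day 17 × 28 + 1 = 477, which few patients may reach. This stands as a limit on size. The Cycle 9 start narrows the contrast to 4 against 10, and through Cycle 9 there is then no difference.

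A third is that the disturbed table layout weakens confidence. It affects the lines above, but the cycle label and the footnote are both intact.

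The safety reply has most weight. At 481 ms or more both drugs are held until QTcF falls below 481 ms. ECGs follow 7 and 14 days after resumption, and recurrence at 501 ms or more ends treatment. Unscheduled and end-of-treatment ECGs apply regardless. Section 1.2.1.4.1 reports that QT changes appear early and then stay stable or improve. These safeguards limit the harm, but none sets a routine frequency after Cycle 6.

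The 0 to 5 patient range is also open to challenge: a clinical benefit rate is not a measure of staying on treatment, and reported QT prolongation is not the same as a QTcF of 481 ms. It shows scale only, and the conclusion does not depend on it.

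**Conclusion.** The concern holds. Table 7-5 contains two incompatible pre-dose ECG frequencies for patients with earlier QTcF prolongation: 4 against 12 ECGs over Cycles 7 to 18, or 4 against 10 if the footnote starts at Cycle 9. The counts rest on 28-day cycles without delay and on reading the footnote literally. Separately, Section 7.2.2.6.1 names the wrong table for managing a QTcF of 481 ms or more, although Table 6-9 can be found by its title.

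The consequence is a minor patient-safety inconsistency affecting an unknown and probably small number of patients (0 to about 5 of 79 under the stated assumptions). The efficacy analyses are not affected. It should be corrected because these are operative safety instructions and the correction is simple.

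**What to change.** 1. Rewrite the Table 7-5 row to match footnote c. For patients with QTcF of 481 ms or more before Cycle 7: pre-dose ECG on Day 1 of every cycle from Cycle 7, plus 2 h post-dose on Day 1 of Cycles 9, 12, 15, 18, etc. The sponsor should confirm the Cycle 7 start, which the documents do not state outright.
2. Keep the row's single 12-lead type, and add an exception for cases where Table 7-5 states otherwise to the sentence in 7.2.2.6.1 that begins "Standard triplicate 12-lead ECGs will be performed after the patient has been resting for 5-10 minutes prior to each time point indicated in" Table 7-5.
3. In the same section, change the reference for QTcF of 481 ms or more from Table 6-7 to Table 6-9.

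**Cost.** One table row and two short wording corrections. For a patient treated through Cycle 12, the new schedule has 6 pre-dose + 2 post-dose = 8 time points against 2 in the row as read, so at most 6 extra single ECGs. If a 2 h line was lost from the row, the comparison is 8 against 4, so 4 extra. All fall at Day 1 visits that already take place, with a stay of about 2 h at Cycles 9 and 12.
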